4.5.2. Adverse Events

The following definitions will be used for AEs:

- **Pretreatment AE:** Any AE that starts after providing informed consent, but before the first dose of study intervention (ALXN2050 or placebo)
- Treatment-emergent adverse event (TEAE): Any AE that starts between the start of the first dose of study intervention and up to 30 days after the last dose of study intervention
- Treatment-emergent serious adverse event (TESAE): A TEAE that is serious
- **Post-treatment AEs:** Any AE that starts 30 days or later after the last dose of study intervention

All AEs will be coded using MedDRA version 26.1 or higher and will be summarized by SOC and PT overall, by severity, and by relationship to treatment.

Participants having multiple AEs within a category (eg, overall, SOC, PT) will be counted once in that category. For severity/relationship tables, the participant's highest grade/most related event within a category will be counted.

TEAEs and serious adverse events (SAEs) will be summarized descriptively by treatment group. Percentages will be based on the number of treated participants in the SS within a treatment group. Tables will be sorted by descending frequency of SOC and by descending frequency of PT within an SOC.

Pretreatment and post-treatment AEs will be provided in by-participant listings and will not be included in summary tables.

In addition, AEs that occur after the receipt of additional standard of care therapy will be provided in a separate listing.

4.5.2.1. Overall Summary of AEs

The following event subcategories will be summarized by treatment group for each disease cohort separately. The number of events (n) and number and percentage of participants with events (n, %) will be shown.

- TEAEs
- TEAEs leading to withdrawal from the study
- TEAEs leading to study treatment discontinuation
- Related TEAEs
- TEAEs by toxicity grade

The summary will be prepared separately for all AEs and SAEs. Additionally, the number and percentage of participants who died on study will be presented.

Detailed by-participant listings of TEAEs, SAEs, related TEAEs, TEAEs leading to withdrawal from the study, and TEAEs leading to study treatment discontinuation will be provided.

4.5.2.2. AEs and SAEs by SOC and PT

The number of TEAEs and TESAEs and the number and percentage of participants with events will be presented by SOC and PT. Participants are counted once in each SOC and PT. Percentages will be based on the total number of treated participants in the treatment group. SOCs will be listed in descending order of frequency of occurrence.

Additional summary tables stratifying AEs and SAEs by age, gender, and race will also be provided.

4.5.2.3. AEs and SAEs by SOC, PT, and Relationship

The number of TEAEs, TESAEs, and the number and percentage of participants with events will be presented by SOC and PT as described above by relationship (related, not related). If a participant has more than 1 occurrence of an AE, the strongest relationship to study treatment will be used in the summary table. SAEs will be summarized similarly.

4.5.2.4. AEs by SOC, PT, and Severity

The number of TEAEs and the number and percentage of participants with events will be presented by SOC and PT as described above by toxicity grade (Grade 1, Grade 2, Grade 3,

Grade 4, and Grade 5). If a participant has more than 1 occurrence of an AE, the most severe occurrence will be used in the summary table.

4.5.2.5. Deaths and Other Significant AEs

Individual listings will be presented for AEs leading to study treatment discontinuation, AEs leading to withdrawal from the study, meningococcal infections, seizures, and fatal AEs.

4.5.3. Additional Safety Assessments

4.5.3.1. Laboratory Parameters

Laboratory assessments are defined in Protocol Section 10.2.

Observed values and changes from baseline in clinical chemistry, hematology, coagulation, and urinalysis will be summarized descriptively by treatment group at baseline and at each scheduled post-Baseline time point separately for each disease cohort. For laboratory results that can be classified as normal, low, or high based on normal range values, shifts from baseline in classification will be summarized for all study visits. For analysis purposes, laboratory results based upon standardized units will be used.

Box plots will be presented for the following central laboratory parameters by visit: ALT, AST, and creatinine.

In addition, abnormal liver enzyme elevations will be addressed by a table that presents the counts and percentages of participants who met any of the following criteria by treatment group at baseline, at each scheduled post-Baseline time point, and during treatment separately for each disease cohort:

- $3\times$, $5\times$, $10\times$, and $20\times$ ULN elevations of AST, ALT.
- 1.5× ULN elevation of ALP.
- Elevation of bilirubin ($> 2 \times ULN$).
- Elevation of ALT ($> 3 \times ULN$) accompanied by elevated bilirubin ($> 2 \times ULN$).
- Elevation of ALT (> 3×ULN) accompanied by elevated bilirubin (> 2× ULN), without elevated ALP, that is, ALP< 2× ULN.

A listing of ALT, AST, total bilirubin, and ALP at all visits will be generated for all participants who met any of the above criteria. Data from local laboratory will not be included in the analysis, except liver enzyme elevations when unit and ULN are available. All central and local laboratory data will be presented in listings, and a specific listing of abnormal results will be provided.

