Figure 2:	Study Design Schematic (IgAN Cohort)	18

VERSION HISTORY

This statistical analysis plan (SAP) for Study ALXN2050-NEPH-201 is based on Protocol Amendment 3.0, dated 21 Feb 2024.

SAP Version	Version Date	Change	Rationale
1.0	23 Nov 2022	Not applicable	Original version.
2.0	10 May 2023	Included the option to perform an early interim analysis	For Phase 3 planning purposes.
		Other minor edits	For clarity.
3.0	12 Nov 2024	Deleted data presentation for Safety Follow-up Period	Safety Follow-up Period is not a treatment period.
		Revised the derivation of the primary endpoint	Visit window is changed.
		Added ALXN2050 Total group into data presentation	To evaluate the overall ALXN2050 treatment effect.
		Changed terminologies: "background therapy" to "allowed concomitant therapy" and "rescue therapy" to "additional standard-of-care therapy"	To align with EU CTR requirements.
		Added an analysis of abnormal liver enzyme elevations	To evaluate drug-induced liver injury.
		Added a sensitivity analysis due to dosing pause	Screening, enrollment, and study intervention administration have been temporarily paused as of 06 September 2024.
		Other minor edits	For minor corrections.

APPROVAL SIGNATURES

Biostatistics	Date dd Mmm yyyy
Biostatistics	Date dd Mmm yyyy
	Date dd Mmm yyyy

LIST OF ABBREVIATIONS

Abbreviation	Definition
AE	adverse event
ALP	alkaline phosphatase
ALT	alanine aminotransferase
AP	alternative pathway
AST	aspartate aminotransferase
ATC	anatomical therapeutic chemical
Bb	Bb fragment of complement factor B
bid	twice daily
BLQ	below the limit of quantification
Clq	complement component C1q
C3	complement component 3
C4	complement component 4
CDF	cumulative distribution function
CI	confidence interval
CNI	calcineurin inhibitor
COVID-19	coronavirus disease 2019
CRR	complete renal response
cTTO	composite time trade-off
CV	coefficient of variation
CV%	coefficient of variation percentage
dsDNA	double-stranded DNA
EC	exclusion criteria
ECG	electrocardiogram
eCRF	electronic case report form
eGFR	estimated glomerular filtration rate
EQ-5D-5L	5-level EuroQol-5 Dimensions
FACIT-Fatigue	Functional Assessment of Chronic Illness Therapy – Fatigue Scale
FAS	Full Analysis Set
FD	factor D
GM	geometric mean
GMR	geometric mean ratio
hpf	high power field
IC	inclusion criteria
IE	intercurrent event

Abbreviation	Definition	
IgAN	immunoglobulin A nephropathy	
LLN	lower limit of normal	
LN	lupus nephritis	
MAR	missing-at-random	
MCS	Mental Component Summary	

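### Both combined liver criteria test ALT only, so raised AST with raised bilirubin is not counted by arm as a combined event when ALT stays at or below 3×ULN

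*SAP*

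**What the plan says.** The Version History of the SAP records for version 3.0: "Added an analysis of abnormal liver enzyme elevations". The rationale beside it is "To evaluate drug-induced liver injury".

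Section 4.5.3.1 (Laboratory Parameters) describes the result as a table giving "counts and percentages of participants who met any of the following criteria by treatment group", at baseline, at each scheduled later visit and during treatment, separately for the two cohorts. It lists five criteria:

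1. 3×, 5×, 10× and 20× "ULN elevations of AST, ALT".
2. ALP at 1.5×ULN.
3. "Elevation of bilirubin" above 2×ULN.
4. ALT above 3×ULN "accompanied by elevated bilirubin" above 2×ULN.
5. "Elevation of ALT (> 3×ULN) accompanied by elevated bilirubin (> 2× ULN), without elevated ALP, that is, ALP< 2× ULN".

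The same section adds a listing: "A listing of ALT, AST, total bilirubin, and ALP at all visits will be generated for all participants who met any of the above criteria". It also lets local laboratory results into the liver analysis when the unit and ULN are known, although other local results are kept out of the analyses.

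**The concern.** The first criterion puts AST and ALT on the same footing. The fourth and fifth then drop AST without giving a reason. These two are the only criteria in the table that tie a transaminase elevation and a bilirubin elevation to the same participant, and the table was added for the purpose of evaluating drug-induced liver injury.

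At stake is a count by arm. If the transaminase that crosses the threshold is AST and not ALT, the combined rows can show no event in an arm where one participant had both elevations. SAP Section 4.5.2.5 does not compensate: its individual listings name meningococcal infections, seizures, fatal AEs and AEs leading to discontinuation or withdrawal, but no liver category. Section 4.5.3.1 is therefore the SAP's dedicated liver output.

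**Working it through.** The plan states no figure to reproduce here. The check sets the criteria side by side and follows a participant through them.

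**Which analytes each criterion uses (SAP 4.5.3.1)**

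| Criterion | ALT | AST | Bilirubin | ALP |
|---|---|---|---|---|
| 1. Enzyme at 3×, 5×, 10×, 20×ULN | yes | yes | – | – |
| 2. ALP at 1.5×ULN | – | – | – | yes |
| 3. Bilirubin > 2×ULN | – | – | yes | – |
| 4. Combined | yes | **no** | yes | – |
| 5. Combined, ALP < 2×ULN | yes | **no** | yes | yes |

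No other section of the SAP pairs AST with bilirubin. Protocol Section 9.4.7.3 (Clinical Laboratory Tests) has only observed values, changes from baseline and shifts, one analyte at a time.

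**Where a participant with bilirubin > 2×ULN is counted**

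| Pattern | Criterion 1 | Criterion 3 | Criterion 4 | Criterion 5 | Listing |
|---|---|---|---|---|---|
| ALT > 3×ULN, any AST | yes | yes | yes | if ALP < 2×ULN | yes |
| AST > 3×ULN, ALT ≤ 3×ULN | yes, through AST | yes | **no** | **no**, whatever the ALP | yes |

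The gap is the second line alone. When ALT is also above 3×ULN the participant is in the combined row, and the AST value makes no difference.

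**Can the combination be recovered from the separate rows?** Suppose that, in an arm of n participants, a have AST > 3×ULN and b have bilirubin > 2×ULN. The number with both lies between max(0, a + b − n) and min(a, b). To illustrate, take the LN 180 mg arm, n = 30 (Protocol Table 8), with a = 1 and b = 1:

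- lower limit: max(0, 1 + 1 − 30) = max(0, −28) = 0;
- upper limit: min(1, 1) = 1.

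The two rows therefore fit either no combined case or one. They settle the matter only in special cases, for example when a or b is 0 and the upper limit is 0. The values a = b = 1 are illustrative and are not a forecast.

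**Effect of accepting either enzyme.** Anyone with ALT > 3×ULN satisfies ALT or AST > 3×ULN. Every participant counted under criteria 4 and 5 as written would stay counted, so the change can only add cases.

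**The case against.** The best case for leaving the text alone has four parts.

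*The case is already visible.* The participant in question meets criteria 1 and 3, is counted under both, and so triggers the listing, which shows ALT, AST, total bilirubin and ALP at every visit. With planned arms of 8 to 30 (Protocol Table 8), reading such a listing is practical. This stands, and it rules out a stronger reading. A reader might infer that raised AST with raised bilirubin is missing from the table, or lost to the report. The documents do not support that: both elevations are counted in their own rows, and the listing puts them together. What remains is narrower. The same listing is also triggered by an isolated ALP or bilirubin elevation, so the case must be picked out by eye, and no count or percentage by arm results.

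*The rule is a legitimate choice.* Nothing in either document says that the combined rule must accept AST. Exclusion criterion 9 in Protocol Section 5.2.1 likewise names ALT and direct bilirubin and sets no AST limit. A sponsor may prefer ALT as its liver marker. It is true that there is no contradiction, only a definition narrower than the row above it. But an entry rule applied at Screening does not justify a narrower count of events on treatment, and the SAP gives no reason for dropping AST.

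*Nothing hangs on these rows.* SAP Section 4.5 plans no formal safety testing, and no stopping, dosing or eligibility rule refers to them. An independent DMC reviews safety data (Protocol Section 9.7), and clinically significant laboratory findings are recorded as AEs unless explained by the underlying disease (Protocol Sections 8.2.4 and 10.3.1). This stands and bears on severity.

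*The frequency is unknown.* A reader might be tempted to express one missed participant as a percentage of a small arm. That is only one divided by the arm size. It would be the same for any single event in any safety table and says nothing about how often AST passes 3×ULN while ALT does not. The documents give no such rate, so none is offered here.

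**Conclusion.** The point holds in a limited form. Both combined criteria in SAP Section 4.5.3.1 are ALT only. A participant with AST above 3×ULN, bilirubin above 2×ULN and ALT at or below 3×ULN is not counted by arm as a combined event, in an analysis added to evaluate drug-induced liver injury. The participant's elevations are tabulated separately and listed, so the loss is one of summary and not of data.

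The expected number of such participants cannot be derived from the documents and is likely small. Sample size, alpha and efficacy analyses are untouched. This is a minor improvement.

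The conclusion assumes that the table is programmed as the criteria are written. SAP Section 1 leaves table specifications to a separate Data Presentation Plan, which is not among the documents. If that plan already uses either enzyme, only the SAP wording needs to be brought into line.

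**What to change.** In both combined criteria of SAP Section 4.5.3.1, change *ALT (> 3×ULN)* to *ALT or AST (> 3×ULN)*, leaving the bilirubin and ALP conditions as they are. If the sponsor wants to keep the ALT-only definition, retain those two rows and add two matching ALT-or-AST rows beneath them, so that both counts are shown. Make the same change in the table specifications.

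The cost is trivial programming. AST is a required analyte (Protocol Table 13) and already feeds the single-enzyme row, the box plots and the listing, so no new data, visits or analyses are needed.

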4.5.3.2. Vital Signs

Vital signs will include systolic and diastolic blood pressure (mmHg), heart rate (beats per minute), respiratory rate (breaths per minute), temperature (degrees Celsius [°C] or degrees Fahrenheit [°F]), and pulse oximetry (%).

Observed values as well as changes from baseline vital signs (blood pressure, heart rate, respiratory rate, and temperature) will be summarized descriptively at each time point by treatment group separately for each disease cohort.

A listing of vital signs will be presented for each disease cohort by treatment group, participant, vital sign, and visit.

4.5.3.3. Electrocardiograms

By-participant data listings of ECG parameters will be provided separately for each disease cohort. ECGs will be evaluated and summarized as normal, abnormal not clinically significant, or abnormal clinically significant.

A shift of overall interpretation from baseline to worst on-study ECG table will be presented for ECG results. Observed values and change from baseline in ECG intervals (PR, RR, QT, and QTc) will be summarized descriptively at baseline and each scheduled post-Baseline time point. QT interval will be corrected for heart rate using Fridericia's formula (QTcF).

4.5.3.4. Physical Examinations

The types and the list of physical examinations are specified in Protocol Section 8.3.1. Adverse changes from baseline in physical examination findings will be classified as AEs and analyzed accordingly. Abnormal physical examination results will be summarized by visit for each treatment group for the SS.

4.6. Other Analyses

4.6.1. Other Variables and/or Parameters

This study will also include PK analysis, PD analysis, COVID-19-related analysis, and subgroup analysis as described in the following sections.

4.6.2. PK/PD Analysis (Both Cohorts)

The SS will be used for PK concentration listings and individual figures, and the PK Analysis Set will be used for PK parameter listings, summary tables, and mean figures.

4.6.2.1. Plasma PK Concentrations

Individual plasma concentrations of ALXN2050 will be presented in data listings and summarized separately using descriptive statistics (N, n [nonmissing values within the population], arithmetic mean, SD, CV%, median, minimum, and maximum) by treatment group, day, and scheduled time point. Individual plasma concentrations of ALXN2050 will be plotted for each participant by actual time (in days) for both treatment periods on both linear and semilogarithmic scales. Mean plasma concentrations of ALXN2050 versus nominal time (in days) will be plotted for both treatment periods on both linear and semilogarithmic scales and with active treatment groups overlayed on the same plot.

Plasma concentrations of ALXN2050 will be reported to 3 significant figures in summary statistics except for CV%, which will be reported to 1 decimal place, and N and n, which will be reported as an integer.

Plasma concentrations that are below the limit of quantification (BLQ) will be treated as zero for calculation of descriptive statistics. When all concentrations are BLQ for a time point, the mean will be presented as BLQ, and the SD and CV will be reported as not applicable, otherwise the calculated mean will be presented.

4.6.2.2. Plasma PK Parameters

Plasma PK parameters of ALXN2050 will be presented in data listings and summarized separately using descriptive statistics (number of observations, arithmetic mean, SD, CV, geometric mean, geometric CV, median, minimum, and maximum) by treatment group and day.

4.6.2.3. PD Analysis

The SS will be used for PD listings and individual figures, and the PD Analysis Set will be used for PD summary tables and mean figures.

The predose sample will be classified as the baseline value. Individual absolute values and change from baseline in serum alternative pathway (AP) activity and plasma Bb fragment of complement factor B (Bb) concentrations will be presented in data listings and summarized separately using descriptive statistics (N, n [nonmissing values within the population], arithmetic mean, SD, CV%, median, minimum, and maximum) by treatment group, treatment period, day, and scheduled time point.

Individual absolute values and change from baseline in serum AP activity and plasma Bb concentrations will be plotted for each participant by actual time (in days). Mean change from baseline in serum AP activity and plasma Bb concentrations will be plotted by nominal time (in days) continuous for both periods and with all treatment groups overlayed on the same plot.

Missing concentrations will be excluded from all calculations and PD analyses.

Serum AP activity and plasma Bb concentration will be reported to 3 significant figures in summary statistics except for CV%, which will be reported to 1 decimal place and N and n, which will be reported as an integer.

4.6.2.4. Population PK and PK/PD Analysis

Details of population PK modeling as well as PK/PD modeling will be presented in a separate analysis plan. Results from the population PK/PD analyses will be presented in a separate report.

4.6.3. COVID-19-Related Analysis

The following COVID-19 related data will be collected in this study:

- Modified and missed study visits (and COVID-19-related reasons)
- Discontinuations impacted by COVID-19
- COVID-19 exposure
- AEs related to COVID-19
- Protocol deviations related to COVID-19 (visit performed remotely, visit not done, visit procedures not done, laboratory draws missed due to COVID-19, site staff not available to see study participants)

A listing of all participants affected by these COVID-19-related study disruptions will be provided by participant identifier and investigative site, including a description of the COVID-19 related study disruption.

The number of participants with missed study visits and the reasons for missed study visits (COVID-19-related or other) will be summarized by treatment groups and overall. In addition, the number of participants with modified study visits and the reasons for modified study visits (COVID-19-related or other) will be summarized by treatment group and overall. Similarly, the number of participants with modified study visits and the ascertainment method for the modified visit will be summarized by treatment group and overall. A by-participant listing of visit status and assessment ascertainment for participants with modified visits will also be produced.

To assess the impact of change in endpoint ascertainment, descriptive statistics of the primary and key secondary endpoints by method of assessment (in-clinic versus alternative method) will be provided using the FAS.

The number of participants with known exposure to COVID-19 will be summarized for pretreatment known exposure and treatment-emergent known exposure by treatment group and overall. A by-participant listing of participants with COVID-19 known exposure or diagnosis will also be produced.

An overall summary table of TEAEs related to COVID-19 will be presented. In addition, the number of TEAEs related to COVID-19 and the number and percentage of participants with TEAEs related to COVID-19 will be presented by SOC and PT.

Protocol deviations related to COVID-19 will be summarized with the overall protocol deviations as specified in Section 6.2.6.

4.6.4. Subgroup Analyses

Summaries of the primary efficacy endpoint will be presented by the following subgroups for both cohorts:

- Age at Screening (18 to 65 years, > 65 years)
- Sex (female, male)
- Baseline eGFR ($\leq 60, > 60-90, > 90 \text{ mL/min/}1.73 \text{ m}^2$)
- Baseline C3/C4 (at least 1 C3/C4 low, no low C3/C4) Assessment method (in-clinic or alternative method)
- Concomitant therapy with SGLT-2 inhibitors (Yes, No), optional for LN cohort

For the LN cohort, summaries of the primary efficacy endpoint will be presented by the following additional subgroups:

- Duration of disease (≤ 1 year, > 1 year)
- Race/ethnicity (African American, non-African American)
- Baseline proteinuria ($\leq 3.5 \text{ g/g}$, > 3.5 g/g)
- Corticosteroid induction timing (prior to Screening, during Screening Period)

- LN class based on central pathology (III or III/V, IV or IV/V)
- TMA on renal biopsy based on central pathology (yes, no)
- Disease status (naïve, relapse)
- Baseline renal biopsy activity index based on central pathology (≤ median, > median)
- Baseline renal biopsy chronicity index based on central pathology (≤ median,
 > median)

For the IgAN cohort, summaries of the primary efficacy endpoint will be presented by the following additional subgroups:

- Duration of disease (≤ 1 year, 1-5 years, > 5 years)
- Race (Asian or Other Pacific Islander, non-Asian or Other Pacific Islander)
- Baseline proteinuria (1-2 g/day, > 2 g/day)
- Baseline MEST-C score based on central pathology (M0, M1, E0, E1, S0, S1, T0, T1, T2, C0, C1, C2)
- Baseline C3 staining based on central pathology (presence, absence)
- Assessment method (in-clinic or alternative method)

For the IgAN cohort, summaries of the primary efficacy endpoint by subgroups of baseline MEST-C score and baseline C3 staining will be presented separately for participants with biopsies within 1 year of randomization and for participants with biopsies greater than 1 year before randomization if feasible based on sample size.

Given that the number of participants in some subgroups may be limited, subgroup categories may be combined as appropriate. Otherwise, the subgroup analysis may not be performed if deemed infeasible based on sample size.

Forest plots will be produced showing the results of the primary efficacy endpoint (percentage change in proteinuria from baseline to Week 26) with means and corresponding CIs for each subgroup described above.

